9.2.1.2 Other Secondary Efficacy Endpoints

The analysis for the key secondary endpoint, CFB in Hb concentration at Week 12 (MI), will be repeated for the secondary endpoints: CFB in Hb concentration at Week 12 (MI) in subjects with baseline Hb <9.5 g/dL; CFB in Hb concentration at Week 4 (MI); and, CFB in Hb concentration at Week 4 (MI) in subjects with a baseline Hb <9.5 g/dL.

Two dichotomous variables, each representing response for the magnitude rise in Hb from baseline, will be calculated for each visit during the Treatment Period from the Hb concentration data. Those subjects with a rise in Hb from baseline of at least 1g/dL will be classified as "Hb rise responders" for the first variable; those subjects with a rise in Hb from baseline of at least 2g/dL will be classified as "Hb rise responders" for the second variable. Separate logistic regression models will be fitted to each of the Hb rise responders at Week 12 variables (secondary endpoints) using an MI approach for the ITT populations. Each model will include terms for the effects of treatment, baseline Hb (below the observed median or at least the observed median), and IBD subgroup. A hypothesis test of the null hypothesis of inferiority for ferric maltol responder rate compared to IV Iron responder rate will be considered for each Hb rise responder secondary endpoint using a non-inferiority margin of 20%. No formal statistical significance level to declare non-inferiority (i.e., rejection of the null hypothesis) of ferric maltol to IV Iron is defined, as CIs and p-values will be presented for descriptive purposes only. The p-value in testing the aforementioned hypotheses will be calculated as described in the primary analysis ([Section 9.1.1](#)).

The above analysis will be repeated for the secondary endpoints: proportions of subjects with baseline Hb <9.5 g/dL that achieve an increase in Hb concentration of ≥ 1 or ≥ 2 g/dL at Week 12; proportions of subjects who experience a change from baseline in Hb concentration ≥ 1 or ≥ 2 g/dL at Week 4 (MI); and, proportions of subjects with baseline Hb <9.5 g/dL that achieve an increase in Hb concentration of ≥ 1 or ≥ 2 g/dL at Week 4 (MI). In addition, the above analysis for the Hb normal limit responder at Week 12 key secondary endpoint will be repeated for the secondary endpoints: proportion of subjects with baseline Hb <9.5 g/dL that is within normal limits at Week 12; proportion of subjects with Hb concentration within normal limits at Week 4; and, proportion of subjects with baseline Hb <9.5 g/dL that is within normal limits at Week 4 (MI).

Serum ferritin will be collected at screening (Visit 1), pre-randomization at Visit 2 (baseline assessment), and at each visit over the Treatment Period. The above ANCOVA analysis will be repeated for the CFB in serum ferritin at Week 12 (MI) secondary endpoint. A summary of serum ferritin and CFB in serum ferritin (OC) will be provided using descriptive statistics for each visit (CFB will be presented at each visit during the Treatment Period) by treatment arm. The summary will include the following ANCOVA model estimates: adjusted means (i.e., Least Squares Means [LSMs]) of CFB in serum ferritin at Week 12 for each treatment

arm, the difference in treatment arm LSMs, the corresponding 95% CIs for treatment arm specific LSMs and difference in treatment arm LSMs, and the p-value for significance of the difference in treatment arm LSMs. Normality and homogeneity of variances for the residuals of each ANCOVA model will be assessed using the procedure outlined in [Section 9.2.1.1](#).

9.2.1.3 Long-term Secondary Endpoints

A dichotomous variable, representing anaemia status (anaemic versus non-anaemic), will be calculated for each visit over the Treatment Period. Women with Hb levels greater than 12.0 g/dL and men with Hb levels greater than 13.0 g/dL will be classified as non-anaemic. Separate logistic regression models will be fitted to the long-term secondary endpoints, anaemia status at each visit over Visits 5-7 (OC), for the ITT and PP populations. Each model will include terms to capture the effects of treatment, baseline Hb (below the observed median or at least the observed median), and IBD subgroup. The above hypothesis testing for Hb normal limit responder ([Section 9.2.1.1](#)) will be repeated here for the anaemia status secondary endpoint.

A dichotomous variable, representing status of serum ferritin level relative to the normal limits of serum ferritin, will be calculated for each visit over the Treatment Period. Women with serum ferritin between 10 and 291 ng/ml and men with serum ferritin between 22 and 322 ng/ml will be classified to be within normal limits of serum ferritin. Those subjects with serum ferritin within the normal limits will be classified as "ferritin normal limit responders". Separate logistic regression models will be fitted to the long-term secondary endpoints, ferritin normal limit responder at each visit over Visits 5-7 (OC), for the ITT and PP populations. Each model will include terms to capture the effects of treatment, baseline Hb (below the observed median or at least the observed median), and IBD subgroup. The above hypothesis testing for rise in Hb responder ([Section 9.2.1.2](#)) will be repeated here for the serum ferritin normal limit responder secondary endpoint.

Separate summaries will be provided for each of the binary long-term secondary endpoint variables defined above. Each secondary endpoint will be summarised using descriptive statistics by visit over the Treatment Period for each treatment arm and overall, utilizing all available data (i.e., OC approach). Each summary will also present the corresponding logistic regression model adjusted difference in proportions (risk difference) of secondary endpoint Hb responders between the two treatment arms, the corresponding [Delta Method derived] adjusted 95% CI for the difference in proportions, and the p-value from testing the null hypothesis of inferiority in risk difference with non-inferiority margin 20%. Finally, each summary will also present the appropriate estimated logistic regression model adjusted odds ratio of secondary endpoint at Visits 5-7 (OC) between the two treatment arms and corresponding 95% CI for the odds ratio.

Any patients who are in the PP population but have major deviations after Week 12 will be excluded from the PP analyses of the long-term secondary endpoints.

10 PHARMACOECONOMIC ANALYSES

Unless otherwise noted, the ITT population will be used for all analyses, summaries, and listings of pharmacoeconomic endpoints.

10.1 Medical Outcomes Study 36-item Short Form (SF-36)

The SF-36 is a multipurpose, proprietary health survey with 36 questions (www.sf-36.org). It was constructed to survey health status in the Medical Outcomes Study and designed for use in clinical practice and research, health policy evaluations, and general population surveys. The SF-36 includes one multi-item scale that assesses eight health concepts (components):

- Limitations in physical activities because of health problems (SF-36 Physical Functioning Component);
- Limitations in social activities because of physical or emotional problems (SF-36 Social Functioning Component);
- Limitations in usual role activities because of physical health problems (SF-36 Role-Physical Component);
- Bodily pain (SF-36 Bodily Pain Component);
- General mental health (psychological distress and well-being [SF-36 Mental Health Component]);
- Limitations in usual role activities because of emotional problems (SF-36 Role-Emotional Component);
- Vitality (energy and fatigue [SF-36 Vitality Component]); and
- General health perceptions (SF-36 General Health Component).

These eight health component scales can be further summarised into two summary scores, the SF-36 Mental Component Score (MCS) and the SF-36 Physical Component Score (PCS).

The survey was constructed for self-administration by persons 14 years of age and older, and for administration by a trained interviewer in person or by telephone. The SF-36 survey will be administered at study visits as indicated in the schedule of assessments ([Table 1](#)), commencing pre-randomization at Visit 2. The SF-36 survey will be completed by the subjects in their native language. Missing values for each of the 36 items of the SF-36 will employ a LOCF approach in ITT analyses up to Week 12.

The process of computing SF-36 component scales involves several steps [4]. First, 10 items of the survey are reverse-coded. Next, component-specific raw scales are formed by way of simple summation over the item scores for the appropriate health component of the SF-36. The component-specific raw scales are then transformed to range between 0 and 100, followed by a norm-based (z-score) transformation.

The latter transformation is carried out such that each scale is mapped to the scale of the 1998 general United States (US) population [4]. The two summary scores, MCS and PCS, are computed by aggregating norm-based component scores using factor score coefficients from the 1990 general US population [4]. The aggregated summary scores are standardized to have a mean of 50 with a standard deviation of 10, in the general 1998 US population [4]. The full SF-36 scoring algorithm is published in [4] and is the approach we take here to score the SF-36. A summary of each of the 8 subscales and the 2 summary scores will be presented using descriptive statistics by visit (OC) for each treatment arm and overall.

The change from baseline (CFB) in each of the 8 SF-36 component subscales and the 2 summary scores will be calculated for each visit during the Treatment Period (BOCF) and analysed with separate ANCOVA models. Each ANCOVA model will include terms for treatment arm, baseline Hb (below the observed median or at least the observed median), and IBD subgroup. A hypothesis test for the treatment effect of ferric maltol compared to IV Iron will be conducted using differences of adjusted means. Statistical significance in the treatment comparison will be declared if the p-value of the hypothesis test from the ANCOVA model is less than or equal to 0.05. Significance levels will not be adjusted for multiplicity. A summary of CFB in each SF-36 subscale and each summary score will be provided using descriptive statistics for each visit during the Treatment Period (OC and BOCF) by treatment arm. The summary will include the ANCOVA estimates: adjusted means (LSMs) of CFB in each SF-36 component and summary score for each treatment arm, the difference in treatment arm LSMs, corresponding 95% CIs for LSMs and difference in treatment arm LSMs, and the p-value for the comparison of treatment arm LSMs. Normality and homogeneity of variances for the residuals of each ANCOVA model will be assessed using the procedure outlined in [Section 9.2.1.1](#).

A data listing of the SF-36 questionnaire will be presented by visit and subject.

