3 STUDY DESIGN

3.1 Overall Study Design

This study will be a Phase 3b, multicentre, open-label, active-controlled, randomized, parallel group prospective study to compare the efficacy and safety of ferric maltol to IV Iron in subjects with inflammatory bowel disease. A total of 242 subjects from 35-45 European sites and around 18 United States sites will be randomized at a ratio of 1:1 to the two treatment arms of this study.

The randomization will be stratified according to screening Hb (<10g/dL or ≥ 10g/dL for Female; < 11g/dL or ≥ 11g/dL for Male) and by IBD subgroup (ulcerative colitis [UC] or Crohn's disease [CD]). Subjects who are re-screened will have their re-screen Hb substituted in lieu of screening Hb for purposes of determining the strata for randomization.

Protocol amendment 7.0 updated the study duration from 52 weeks to 12 weeks. For subjects who entered the study under the previous protocol for the 52 weeks open-label design and completed their study beyond the 12 weeks treatment period, the next scheduled visit will be their End of Study Visit. Otherwise, subjects after the eligibility screening period will enter a 12 weeks treatment period.

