3.2.2 Treatment Period (Visits 2-7)

The Treatment Period begins on the day for which the subject receives their first dose of a study drug (Visit 2/Day 0) and ends on the day corresponding with Visit 7 for those subjects enrolled prior to protocol amendment 7.0, and the day corresponding with Visit 4 for those subjects enrolled under protocol amendment 7.0. Eligible subjects will be randomized in a 1:1 ratio to receive treatment with either oral ferric maltol or intravenous iron.

Subjects randomized to the oral ferric maltol treatment arm will self-administer study medication twice daily; first thing in the morning at least 1 hour before food and concomitant medications, and last thing at night before bed at least 2 hours after food and concomitant medications. Capsules must be taken on an empty stomach with water only. There should be at least an 8-hour gap between doses. These subjects will maintain treatment with oral ferric maltol for the duration of the Treatment Period.

Subjects randomized to the intravenous iron treatment arm will receive IV Iron in accordance with the dosing instructions as per the local summary of product characteristics (SPC)/Prescribing Information (PI). Initial dosing will be as per local SPC/PI, with the number of IV Iron doses administered being calculated based on the subject's starting Hb and weight. For ongoing treatment decisions, ferritin will be measured at Visits 4 (Week 12) and Visits 5 and 6 (Week 24, and Week 36) for patients prior to protocol amendment 7.0. Subjects continuing after Week 12 who are iron deficient (ferritin below 100ng/mL) at any of Visits 4-6 will receive additional IV Iron doses according to the formula in the local SPC/PI.

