8 Follow up is conducted by telephone, unless the subject has an ongoing AE that requires physical examination or investigations for assessment/management. Visit 8 will take place 14 days after Visit 4 (week 12/Early Termination) unless subject discontinued treatment early and end of study/Week 52 assessments occurred 14 days or more after the last dose.

9 Visit Windows: Maximum of 14 days between screening and randomization. Subjects randomized to IV Iron must complete Visit 2 ideally on the day of randomisation or within 5 days. The subject must visit to complete:

Visits 3 and 4: +/- 1 week relative to date of Visit 2/first dose administered

Visit 4 to 7: +/- 1 week relative to date of Visit 2/first dose administered

Visit 8: 14 days (+5 days) after Visit 4 (unless subject discontinued treatment early and end of study/Week 12 assessments occurred 14 days or more after the last dose).

10 SF36 to be administered at Week 0 (baseline), and Week 12, 24, 36, and 52.

11 SF36 is not collected at this visit.

- 12 For CD subjects, a CDAI diary card will be provided at Screening, for completion over the 7 days prior to scheduled Visit 2. The screening haematocrit value will be used for the screening CDAI calculation to assess eligibility prior to randomization and will also count as the baseline CDAI value. For CD subjects, CDAI diary cards will then be provided at Visits 3 and 4. Subjects who went beyond week 12 will receive CDAI diary at Visit 5 and 6 for completion over the 7 days prior to the scheduled dates of Visit 4, 5, 6 and 7.
- 13 Retained serum and plasma samples will only be collected from trial subjects at those Investigator sites who have suitable freezer facilities for storage of the samples at -70°C/-80°C, prior to subsequent periodic shipping to the central laboratory on dry-ice. Detailed instructions will be provided in the Laboratory Manual.
14. Dispense/Administer study drug: based on the randomization stratification subjects will receive FCM/Ferric Maltol on Visit 2. If subjects went beyond Visit 4 (Week 12) and their treatment period will be continuing according to previous protocol until the next scheduled visit.
15. Visit 5 (Week 24) will only occur if subjects went beyond Visit 4 according to previous protocol, otherwise this will be the End of Study Visit.
16. Visit 6 (Week 36) will only occur if subjects went beyond Visit 5 (week 24) according to previous protocol, otherwise this will be the End of Study Visit.

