7.1.2 Non-Date Values

Every effort will be made to obtain required data at each scheduled evaluation from all subjects who have been enrolled. Missing values for the primary efficacy endpoint of Hb responder (i.e., a subject who either has at least 2g/dL rise in Hb from baseline or has shift from baseline of anaemic to non-anaemic status) at Week 12 will be imputed using a Multiple imputation approach for the primary efficacy analysis on the ITT population. If the value of Hb is missing, multiple imputation based on pre-treatment visits will be used in the baseline and multiple imputation based on post-treatment visits will be used to determine the post-baseline value to be used in the primary efficacy endpoint analysis on the ITT population.

As additional sensitivity analyses, missing values for the primary efficacy endpoint on the ITT population will also be imputed using a Last Observation Carried Forward (LOCF) approach up to Week 12.

Missing values for efficacy variables will be replaced for the secondary endpoint analyses, as follows:

- For the key endpoint, 'Hb concentration within normal limits', subjects not returning to a follow-up visit will be assumed to have Hb concentration not within normal limits.
- For the endpoint, 'Increases in Hb concentration of $\geq 1\text{g/dL}$ ', subjects not returning to a follow-up visit will have their Hb concentration imputed using multiple imputation.
- For the endpoint, 'Increases in Hb concentration of $\geq 2\text{g/dL}$ ', subjects not returning to a follow-up visit will have their Hb concentration imputed using multiple imputation.

Missing values for the long-term secondary efficacy endpoints, normalization of Hb at 6 and 12 months and normalization of ferritin at 6 and 12 months, will not be imputed.

Missing values for the SF-36 pharmacoeconomic analysis will be imputed by a LOCF approach up to Week 12. Missing values for all other pharmacoeconomic analyses will be kept as missing.

Safety data will be used according to availability, with no imputation for missing data.

Imputation of data values will only be carried out, where indicated, for computational purposes and fitting of models. Actual data values, as they appear in the original CRFs, will be shown in the data listings.

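### SF-36 change is assigned BOCF at every visit in SAP Section 10.1 but LOCF only to Week 12 elsewhere; read literally, visits cancelled by amendment 7.0 count as zero change

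*SAP*

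**What the plan says.** Three statements in the SAP govern missing SF-36 data.

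- Section 7.1.2: "Missing values for the SF-36 pharmacoeconomic analysis will be imputed by a LOCF approach up to Week 12".
- Section 10.1, paragraph on administration of the survey: "Missing values for each of the 36 items of the SF-36 will employ a LOCF approach in ITT analyses up to Week 12".
- Section 10.1, paragraph on the ANCOVA: change in the 8 subscales and 2 summary scores "will be calculated for each visit during the Treatment Period (BOCF) and analysed with separate ANCOVA models". The accompanying summary is to give "descriptive statistics for each visit during the Treatment Period (OC and BOCF) by treatment arm".

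The schedule of assessments (Table 1, footnote 10) has "SF36 to be administered at Week 0 (baseline), and Week 12, 24, 36, and 52"; footnote 11 confirms that it is not collected at Week 4. Section 3.1 states that "Protocol amendment 7.0 updated the study duration from 52 weeks to 12 weeks" and that subjects already past Week 12 finish at their next scheduled visit. Section 3.2.2 nevertheless says that the Treatment Period "ends on the day corresponding with Visit 7 for those subjects enrolled prior to protocol amendment 7.0"; for subjects enrolled under the amendment it ends at Visit 4 (Week 12).

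Section 10.1 declares significance on the ANCOVA p-values at 0.05, without adjustment for multiplicity. Section 10 of the later post-hoc plan refers pharmacoeconomic analyses back to SAP v3.0, so it leaves these statements as they are.

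**The concern.** The statements differ in method (baseline carried forward against last observation carried forward) and in span (every Treatment Period visit against up to Week 12). A programmer cannot follow all three.

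The difference matters because many of the gaps at Weeks 24 to 52 could be administrative. A visit that the sponsor removed by amendment says nothing about the subject's quality of life, so there is no rationale for recording it as a return to baseline. Doing so would dilute the reported differences in adjusted means and narrow their intervals around the diluted value. It would also depart from the plan's own handling of comparable data: Section 7.1.2 leaves the 6- and 12-month haemoglobin and ferritin endpoints unimputed.

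**Working it through.** **Step 1: what BOCF can mean here.** The term is missing from the abbreviation list. Its only explanation, in Section 9.1.1, is that the screening value replaces a missing baseline haemoglobin. That cannot apply to SF-36, which is first collected at Visit 2. Section 10.1 sets BOCF beside OC as the imputed alternative to observed cases. Baseline observation carried forward is therefore the only workable meaning, and it is assumed below.

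**Step 2: compare the rules by visit.**

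| Visit | Section 7.1.2 and 10.1 (LOCF) | Section 10.1 ANCOVA (BOCF) |
|---|---|---|
| Week 12, whole questionnaire missing | last scheduled value is baseline, change = 0 | change = 0 |
| Week 12, single items missing, or an unscheduled or early-termination questionnaire | item-level or last value carried | may differ |
| Weeks 24, 36, 52 | no imputation | change = 0 |

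The conflict of substance lies after Week 12.

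**Step 3: who is reached.** Section 10.1 computes change during the Treatment Period. For subjects enrolled under amendment 7.0 that period ends at Visit 4, so they receive no value at Weeks 24 to 52. For subjects enrolled earlier it nominally runs to Visit 7, yet Section 3.1 stops them sooner. Only this second group can receive zeros for cancelled visits.

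**Step 4: size with equal shares.** The SAP gives no SF-36 effect, SD or truncated share, so there is no figure of its own to reproduce. Assumptions: mean changes 6 and 1 (difference 5), SD 10, a share f set to zero in both arms, and 121 per arm. The last is an upper bound, since it counts everyone randomised.

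- BOCF difference = (1 − f) × 5
- BOCF variance in an arm with mean change m = (1 − f)(10² + m²) − [(1 − f)m]²
- BOCF SE = √(sum of the two variances / 121)
- Observed-case SE = √(2 × 10² / [121(1 − f)])

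For f = 0.3: variances 77.56 and 70.21; BOCF SE = √(147.77/121) = 1.11; observed-case SE = √(200/84.7) = 1.54. For f = 0.7: variances 37.56 and 30.21; BOCF SE = √(67.77/121) = 0.75; observed-case SE = √(200/36.3) = 2.35.

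| f | BOCF difference (95% CI) | z | Observed-case difference (95% CI) | z |
|---|---|---|---|---|
| 0.3 | 3.5 (1.33 to 5.67) | 3.17 | 5.0 (1.99 to 8.01) | 3.25 |
| 0.7 | 1.5 (0.03 to 2.97) | 2.00 | 5.0 (0.40 to 9.60) | 2.13 |

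The interval narrows in step with the estimate: the SE ratios are 1.105/1.537 = 0.72 and 0.748/2.347 = 0.32, close to 1 − f. The test statistic hardly moves. Simulation with equal true changes and equal shares of 30%, 50% and 70% (20,000 runs each) gives rejection rates of about 5%. At f = 0.7 the BOCF interval excludes the assumed true difference of 5.

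**Step 5: size with unequal shares.** Let both arms truly change by 5 points, with 40% of one arm and 60% of the other set to zero. The BOCF means are 0.6 × 5 = 3.0 and 0.4 × 5 = 2.0, a false difference of 1.0 point.

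**The case against.** The strongest reply is that BOCF is a leftover label. Section 9.1.1 also attaches it to the Week 12 responder result, although that analysis uses multiple imputation and the following text labels the same result MI. The explicit SF-36 rules limit imputation to Week 12, and the Table 1 footnotes say that later visits occur only if the subject continued, so a cancelled visit is arguably unscheduled rather than missing. This may well be what was intended. It does not settle the matter: the label appears twice in 10.1, once as the counterpart of OC, and Section 3.2.2 still runs the Treatment Period to Visit 7 for the earlier enrolees. If it is a leftover, it still has to come out.

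Two stronger readings are tempting, and the documents do not support them.

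- A reader might infer that the imputed zeros make the standard errors far too small and the p-values invalid. That compares standard errors of two differently scaled quantities. The BOCF standard error is right for the diluted difference, and with equal shares the test keeps about its 5% size.
- A reader might infer that everyone without a Week 24 to 52 visit is scored as unchanged. Section 3.2.2 ends the Treatment Period at Visit 4 for subjects enrolled under the amendment.

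It is also fair to say that the amendment applied to both arms, so cancelled shares may be similar, and that the planned observed-case summaries would let a careful reader see the dilution.

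**Conclusion.** The contradiction is real and unresolved, and its effect is confined to SF-36 at Weeks 24, 36 and 52 among subjects enrolled before amendment 7.0 and stopped early by it. Under the usual meaning of BOCF, the adjusted differences and their intervals would shrink by about (1 − f). The 3.5 to 1.5 point range rests on an assumed 5-point difference and an assumed f of 30% to 70%; neither is in the SAP. With equal shares the damage is to the estimate and interval, not to the error rate. Unequal shares can produce a difference where none exists.

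Severity is modest. SF-36 is a pharmacoeconomic endpoint and the primary non-inferiority conclusion does not depend on it. The point still deserves correction because Section 10.1 declares significance at 0.05 on ten scores per visit and, unlike Section 9.2.1.1 for haemoglobin change, does not call those p-values descriptive.

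**What to change.** State one SF-36 rule:

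- Delete BOCF from both places in Section 10.1.
- At Week 12, run the ANCOVA under the LOCF rule of Section 7.1.2.
- At Weeks 24, 36 and 52, use observed cases only, and classify visits cancelled by amendment 7.0 as not applicable rather than missing.
- Carry the same rule into Table 14.2.8.2, reporting the number of subjects contributing at each visit by arm.

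This changes wording and programming and needs no new data. The cost is fewer subjects and wider intervals at the later visits, which reflects the information actually collected.

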9.2 Secondary Efficacy Analyses

9.2.1 Secondary Analysis

9.2.1.1 Key Secondary Endpoints

The change from baseline (CFB) in Hb concentration at Week 12 (MI) secondary endpoint will be analysed for the ITT population using an analysis of covariance (ANCOVA) model.

For the multiple imputation, the code for implementing the SAS® procedure MIANALYZE to the CFB Hb concentration at Week 12 secondary endpoint is:

```
DATA CFB_Impute; SET MI_out; CFBHbW12 = Week12Hb - baselineHb; RUN;
```

```
PROC SORT DATA = CFB_Impute; BY _Imputation_; RUN;
```

```
PROC REG DATA = CFB_Impute OUTEST = outreg COVOUT;  
  BY _Imputation_;  
  MODEL CFBHbW12 = binarybaselineHb TreatmentArm IBDGroup;  
RUN;
```

```
PROC MIANALYZE DATA = outreg EDF = <complete-data degrees of freedom>;  
  MODELEFFECTS Intercept binarybaselineHb TreatmentArm IBDGroup;  
  ODS OUTPUT ParameterEstimates = parm1;  
RUN;
```

The ANCOVA model will have terms for treatment arm, baseline Hb (below the observed median or at least the observed median), and IBD subgroup. The treatment effect of ferric maltol compared to IV Iron will be considered using differences of adjusted means. No formal statistical significance level in the treatment comparison will be defined, as the p-value from the ANCOVA model will be presented for descriptive purposes only. A summary of CFB in Hb concentration (OC) will be provided using descriptive statistics for each visit over the Treatment Period by treatment arm and overall. The summary will include the following

ANCOVA model estimates: adjusted means (i.e., Least-Square Means [LSMs]) of CFB in Hb concentration at Week 12 for each treatment arm, the difference in treatment arm LSMs, the corresponding 95% CIs for treatment arm specific LSMs and difference in treatment arm LSMs, and the p-value for the difference in treatment arm LSMs. Mean CFB in Hb concentration will be plotted against visit (OC) by treatment arm for the ITT and PP populations.

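### The SF-36 and ferritin change-from-baseline ANCOVAs omit the outcome's own baseline, which costs precision and mishandles chance baseline imbalance

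*SAP*

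**What the plan says.** **SF-36 (SAP v3.0, 10.1).** The outcome is a change score: "The change from baseline (CFB) in each of the 8 SF-36 component subscales and the 2 summary scores will be calculated for each visit". The model is: "Each ANCOVA model will include terms for treatment arm, baseline Hb (below the observed median or at least the observed median), and IBD subgroup". The inference is formal: "Statistical significance in the treatment comparison will be declared if the p-value" is at or below 0.05, and "Significance levels will not be adjusted for multiplicity". The questionnaire is given "commencing pre-randomization at Visit 2", so every scale has a pre-randomisation value.

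**Ferritin (9.2.1.2 of SAP v3.0, repeated in the post-hoc SAP).** "The above ANCOVA analysis will be repeated for the CFB in serum ferritin at Week 12 (MI) secondary endpoint". The model being repeated is the one for change in haemoglobin in 9.2.1.1: "The ANCOVA model will have terms for treatment arm, baseline Hb (below the observed median or at least the observed median), and IBD subgroup". The SAS code there lists the same three terms. The p-value of that model is stated to be descriptive. Ferritin is also measured before randomisation at Visit 2.

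**Nothing elsewhere adds the missing term.** The general covariate rule (6.3) names only IBD subgroup and baseline haemoglobin. Section 10 of the post-hoc SAP sends the reader back to v3.0 for the pharmacoeconomic analyses.

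**The concern.** For change in haemoglobin, baseline haemoglobin is the outcome's own baseline, so the model in 9.2.1.1 does adjust for it, although only as a median split. The same covariate list was then applied to SF-36 and ferritin without substituting their baselines. These two analyses are therefore close to plain comparisons of change scores, with a covariate that may be only weakly related to the outcome.

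Two things are at stake. The confidence interval is wider than it needs to be. And if the arms differ by chance at baseline, the change score does not adjust for that difference correctly. This matters most for SF-36, where each of the ten scores can yield a formal significance statement.

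**Working it through.** **Inputs.** The plan states no power, SD or correlation for SF-36 or ferritin, so it has no figure of its own to reproduce on this point. Its only sample-size figure concerns the primary endpoint (section 4): 108 per arm, raised by 12%, gives 108 × 1.12 = 120.96, i.e. 121. I use n = 121 per arm. Assumptions: rho = 0.3, 0.5 or 0.7; equal SDs at baseline and follow-up; and an SD of 10 for scale, which is the population standardisation of the two summary scores in 10.1.

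**Step 1: precision, SF-36.**
- Variance of the difference, change score without own baseline: 2·SD²·(1 - rho)·2/n
- Variance with own baseline in the model: SD²·(1 - rho²)·2/n
- Ratio (own baseline / plan): (1 + rho)/2
- Relative CI width of the plan's model: √(2/(1 + rho))
- Power of the plan's model at the effect for which the own-baseline model has 80%: Φ(2.80·√((1 + rho)/2) - 1.96)

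| rho | Variance ratio | Reduction | SE, plan | SE, own baseline | Plan's CI wider by | Plan's power |
|---|---|---|---|---|---|---|
| 0.3 | 0.65 | 35% | 1.52 | 1.23 | 24% | 62% |
| 0.5 | 0.75 | 25% | 1.29 | 1.11 | 15% | 68% |
| 0.7 | 0.85 | 15% | 1.00 | 0.92 | 8.5% | 73% |

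**Step 2: does split haemoglobin stand in for the missing term?** I simulated 4,000 trials per setting with the median-split haemoglobin and IBD terms in both models. For rho = 0.3, 0.5 and 0.7 the variance ratios were 0.67, 0.74 and 0.84 when haemoglobin was unrelated to the outcome's baseline. They were 0.66, 0.77 and 0.87 when that correlation was 0.3. It is a poor substitute. The mean estimate under no effect was close to zero for both models in every setting.

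**Step 3: chance imbalance.** Given a baseline difference D between arms, the change score has conditional bias -(1 - rho)·D. A two-standard-error imbalance is 2 × 10 × √(2/121) = 2.57 points. The bias is then -1.80, -1.29 or -0.77 points, and the conditional type I error is 17%, 13% or 10% instead of 5%. At a one-standard-error imbalance it stays just under 5% (4.6%, 4.8%, 4.9%).

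**Step 4: carried-forward SF-36 values.** SF-36 is not collected at Week 4 (Table 1, note 11), so carrying the last observation forward to Week 12 means carrying the baseline. Those subjects have a change of zero. If a fraction m is so imputed and the mean shift is ignored, the effective correlation is m + (1 - m)·rho. With rho = 0.5 and an assumed m of 10%, that is 0.55, the ratio is 0.775, and the reduction falls from 25% to 22.5%. With m = 20% it is 0.60, the ratio is 0.80, and the reduction is 20%.

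**Step 5: ferritin.** Equal SDs are doubtful when one arm receives IV iron. With follow-up SD k times the baseline SD, the ratio is k²(1 - rho²)/(1 + k² - 2·rho·k):
- k = 2, rho = 0.5: 3.00/3.00 = 1.00 (no gain)
- k = 3, rho = 0.5: 6.75/7.00 = 0.96
- k = 3, rho = 0.7: 4.59/5.80 = 0.79

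**The case against.** The strongest reply is that this is an efficiency improvement to analyses of modest rank. SF-36 is a pharmacoeconomic measure that section 14 of SAP v3.0 says was not explicit in the protocol. Change in ferritin is not in the endpoint list of 2.3.2 and inherits a descriptive p-value. Under 1:1 randomisation, regression to the mean is expected equally in both arms, so the comparison is unbiased and overall type I error is kept. Lost precision mainly costs power. All of that stands, and it limits the weight of the point. It does not remove the omission.

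The reply also bears on stronger readings that a reader might infer:
- *That imbalance is left uncorrected.* It is not. Subtracting the baseline removes the full difference, which is too much whenever the slope of follow-up on baseline is below 1. The residual bias has the opposite sign to the imbalance.
- *That results are changed.* The documents hold no SF-36 or ferritin data, so one can say only that an SF-36 significance statement could change.
- *That the SF-36 percentages apply to ferritin.* They rest on equal SDs, and Step 5 shows the gain can vanish.
- *That the repair is entirely free.* The post-hoc SAP follows a clinical study report and lists no SF-36 output, so adding the covariate now would reopen a reported analysis.

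**Conclusion.** The omission is real for SF-36 (v3.0, 10.1, which the post-hoc SAP leaves in force) and for ferritin (9.2.1.2 in both SAPs). The treatment difference remains unbiased over randomisations. What is lost is precision, together with proper conditional adjustment for chance imbalance.

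For SF-36 the variance could be about 35%, 25% or 15% lower at an assumed rho of 0.3, 0.5 or 0.7 with equal SDs, and the gain is smaller the more baseline values are carried forward. For ferritin the gain is unknown and may be near zero. The SF-36 part carries most of the weight, because it is tested formally at 0.05. A reader should not extend the point to the primary endpoint, whose non-inferiority conclusion does not depend on these models.

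**What to change.** - In 10.1, add to each SF-36 model the continuous baseline score of the same scale. Keep treatment arm, IBD subgroup and baseline haemoglobin.
- In 9.2.1.2 of both SAPs, add continuous baseline ferritin to the ferritin model. If ferritin is skewed, use the log scale for both outcome and covariate.
- Where v3.0 results have already been reported, leave them in place and present the extended model beside them as a post-hoc analysis, using the labelling rule in section 6 of the post-hoc SAP.

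The cost is one degree of freedom per model and, for reported results, an additional labelled output. The baseline values are already scheduled for collection.
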